10.8 Electronic medical record data

The following data from the participants' EMR *Sundhedsplatformen* will be collected at V1. Changes in glucose- and cholesterol-lowering medications will be registered at visits V5 and V6 and total number of visits at a diabetologist and diabetes nurse during the study period will be registered at V6.

- Type of diabetes
- Gender
- Date of birth
- Smoking status
- Diabetes duration
- Gastroparesis
- Prescribed insulin, types and dosages
- Prescribed oral antidiabetics, types and dosages
- Prescribed cholesterol lowering medication, types and dosages
- Prescribed other medication and dose or changes in dose of other medication
- Participation in BCC group program previously
- Use of open CGM
- Use of a Free Libre
- Use of an automated bolus calculator

10.9 Other baseline demographics

The following self-administered questions on baseline demographics will be sent out electronically before V1 using the software system REDCap (appendix 13).

- Educational level
- Main occupation
- Use of mathematics in their current or previous profession or in their spare time
- Civil status and household composition
- Yearly income

10.10 Physical activity level

Physical activity level will be assessed using IPAQ SF (appendix 12). Participants will be encouraged to continue their habitual level of physical activity and not to change it during the 24 weeks study period. IPAQ SF will be send electronically before visits V1, V5 and V6.

11 Study visits

The following section describes all visits included in the study. The visits are also schematically presented in table 1. The visits will be conducted by the principle study investigator and study personnel under responsibility of the principle investigator. Examinations are described in section 10. For logistical reasons, windows are allowed for the study visits (\pm 21 days). A detailed visit flow for the study groups is presented in **Figure 2**.

Figure 2 Visit flow

BCC=basic Carbohydrate counting; BP= blood pressure; BW=body weight; CGM=continuous glucose monitoring; DXA=dual-energy-X-ray absorptiometry; V=visit

11.1 Study information

The following procedures will be performed in the following order:

- Short oral patient information by phone
- Written patient information
- Personal meeting for thorough oral patient information
- Invitation to participate in the study after the patient has had time for reflection (at least 24 hours)

11.2 Screening

- A signed informed written consent has been collected before continuing
- A non-fasting blood sample for assessment of HbA1c (screening criteria)
- Screening for study eligibility according to inclusion and exclusion criteria,
- If not eligible for inclusion the cause of screening failure is recorded and explained to the patient
- Participants eligible for inclusion will be registered with an ID code
- Randomization will be performed before the participant is sent home

11.3 V1: Baseline (week -4 to -1)

At visit 1 the following procedures and assessments will be performed in the morning after 8-10 hours fast:

- Collection of fasting blood samples
- Measurement of height, body weight, blood pressure, hip and waist circumference (fasting)
- Pregnancy test (woman only)
- Full body DXA scan (fasting condition)
- A meal is provided for the participant
- Fill in questionnaire concerning demographic data, CPQ, Mathematical literacy test, DDRQOL, PCS, HCCQ, IPAQ SF at V1
- Collection of medical history including registration of glucose- and lipid-lowering medicine
- Instruction in how to fill out the three days of dietary registration forms
- Instruction in how to collect four days of urine sample and how to hand in the sample
- Injection of CGM device and instruction in precautions and how to hand in the CGM
- Instruction in recording four daily PG measurements in six days with CGM

11.4 V2: Start of intervention, day 1 (week 0)

At visit 2 the following procedures and assessments will be performed:

- Measurement of body weight and HbA1c (non-fasting condition)
- Update of glucose- and lipid-lowering medicine
- Standard individual dietary counselling

11.4.1. V2A: Start of intervention, day 1 (week 2) (BCC only)

At visit 2A the following procedures will be performed for participants randomized to the BCC group:

• Day 1 of BCC program in groups according to curriculum

This visit will take place ± 14 days compared to V2

11.5 V3: intervention, day 2 (week 12)

At visit 3 the following procedures and assessments will be performed:

- Measurement of body weight and HbA1c (non-fasting condition)
- Update of glucose- and lipid-lowering medicine
- Standard individual dietary counselling follow-up

11.5.1. V3A: intervention, day 2 (week 4) (BCC only)

At visit 3A the following procedures will be performed for participants randomized to the BCC group:
Day 2 of BCC program in groups according to curriculum

For logistical reasons the visit will take place ± 21 days compared to V2A

11.6 V4: intervention, day 3 (week 20)

At visit 4 the following procedures and assessments will be performed:

- Measurement of body weight and HbA1c (non-fasting condition)
- Update of glucose- and lipid-lowering medicine
- Standard individual dietary counselling

11.6.1. V4A: intervention, day 3 (week 14) (BCC only)

At visit 4A the following procedures will be performed for participants randomized to the BCC group:

• Day 3 of BCC program in groups according to curriculum

For logistical reasons the visit will take place ± 21 days compared to V3A

11.7 V5: After 24 weeks of intervention

At visit 5 the following procedures will be performed in the morning after 8-10 hours fasting:

- Collection of fasting blood samples
- Measurement of body weight, blood pressure, hip and waist circumference (fasting condition)
- Check for pregnancy (women only)
- Full body DXA scan (fasting condition)
- A meal is provided for the participant
- Participants who has not filled in all questionnaires before V5 will be asked to fill in at V5
- Update of glucose- and lipid-lowering medicine
- Instruction in how to fill out the three days of dietary registration forms
- Instruction in how to collect four days of urine sample and how to hand in the sample
- Injection of CGM device and instruction in precautions and how to hand in the CGM
- Instruction in recording four daily PG measurements in six days with CGM

11.8 V6: Follow-up at 48 weeks (24 weeks after intervention completion)

At visit 6 the following procedures will be performed in the morning after 8-10 hours fasting:

- Collection of fasting blood samples
- Measurement of body weight, blood pressure, hip and waist circumference (fasting condition)
- Update of glucose- and lipid-lowering medicine
- Check total number of visits at a diabetologist and diabetes nurse during the study period
- Participants who has not filled in all questionnaires before V6 will be asked to fill in at V6
- A meal is provided for the participant

12 Laboratory analyses

12.1 Laboratory

Laboratory analyses will be performed in the Department of Clinical Biochemistry at SDCC, [name].

The current and emerging biomarkers of total carbohydrate intake and of carbohydrate-rich foods have been developed by University of Copenhagen (Preventive and Clinical Nutrition group, Dept. of Nutrition, Exercise and Sports (NEXS)) and others using equipment available at SDCC (Systems Medicine Group).

12.2 Sample handling

Blood samples will be drawn from all study participants as part of V1 to V6. Blood samples will be drawn and handed according to standard operational procedures (SOPs) specified by the Clinical Biochemical Department at SDCC which is responsible for the collection and analysis of the samples and storage locally until further data analysis. Blood samples in the study will be analysed immediately including plasma HbA1c at V1 in all potential participants since this measurement is used as part of the screening to assess if the patient in eligible for inclusion in the study. The total volume of blood drawn during the 48 weeks is a maximum of 186 ml, with 60 ml drawn at V1, V5 and V6 including 3 x 10 ml for a biobank for future research, as specified in **table 2**. Any remaining samples and left over will be destroyed after conducting the analysis and storing of 30 ml for the biobank for future research.

Visit number	Week number	Max blood volume (ml)
Visit 1	-4 to -1	60
Visit 2	0	2
Visit 3	12	2
Visit 4	20	2
Visit 5	24	60
Visit 6	48	60

Table 2: Maximum volume of blood collected

Urine will be collected as midstream urine spots four times daily (4 x 3 ml) for four days by the participants after V1 and V5 and will be analysed to estimate the albumin-creatinine ratio and metabolomics analysis for excretion of biomarkers related to carbohydrate intake (sucrose, fructose, mannose and lactose) and qualitative markers of common groups of carbohydrate rich foods including vegetables, fruit, whole grain, and possibly potato, beet root, and rice and other intermediate metabolites at SDCC. After the return of urine collections at SDCC, these will be handed according to specific SOPs and stored until further data analysis for determination of metabolic profile (metabolomics analysis) at SDCC. The total volume of urine collected during the 48 weeks is 96 ml, with 48 ml being collected at each of the two visits (including 12 ml at V1 and V5 for a biobank for future research), as specified in **table 3**.

Table 3: Maximum volume of urine collected

Visit number	Week number	Max urine volume (ml)
Visit 1	-4 to -1	48
Visit 5	24	48

The collected blood and urine samples will be used for analysis in the study listed in Table 4.

Visit	Visit 1	Visit 2	Visit 3	Visit 4	Visit 5	Visit 6
Week	-4 to -1	0	12	20	24	48
P-ALAT	Х				Х	Х
P-Albumin	Х				Х	Х
U-Albumin	Х				Х	
P-Alkaline phosphatase	Х				Х	Х
P-C-peptide	Х				Х	Х
P-Cobalamin	Х				Х	Х
P-Creatinine	Х				Х	Х
U-Creatinine	Х				Х	
P-Glucose	Х				Х	Х
P-HbA1c	Х	Х	Х	Х	Х	Х
P-HDL cholesterol	Х				Х	Х
P-Haemoglobin	Х				Х	Х
P-LDL cholesterol	Х				Х	Х
P-Leucocytes	Х				Х	Х
P-Potassium	Х				Х	Х
P-Sodium	Х				Х	Х
P-Thrombocytes	Х				Х	Х
P-Total cholesterol	Х				Х	Х
P-Triglyceride	Х				Х	Х
P-TSH	Х				Х	Х
P-VLDL cholesterol	Х				Х	X
Metabolomics analysis (urine)	Х				Х	
Biobank – plasma	Х				Х	X
Biobank – urine	Х				Х	

Table 4: Analysis of biochemical samples

ALAT = Alanine aminotransferase; HbA1c = Glycosylated haemoglobin; HDL = High-density-lipoprotein; LDL = Low-density-lipoprotein; TSH = Thyroid-stimulating hormone; VLDL = Very-low-density-lipoprotein.

12.3 Storage of samples

Urine samples in the study will be stored and analysed after the last patient's last visit in the study, while blood and urine samples specifically collected for the biobank for future research will be stored in -80 degrees freezer at SDCC, [name].

12.4 Samples for a research biobank and a biobank for future research

A research biobank will be established for some of the samples specified in the current protocol. The aim of establishing the research biobank is to store urine samples from the participants for biochemical analysis after the last patient's last visit in the study. The samples will be kept until 31.12.2022 where the final analysis and study will be finished. At visits V1 and V5 urine samples of maximum 48 ml will be collected (96 ml in total during the study period) and stored in the research biobank. Any urine left in the research biobank after all relevant biochemical measurements have been performed will be destroyed.

In addition to the research biobank, a biobank with additional blood and urine samples from the participants for use in future research within the area of diabetes not specified in the present protocol will be established. The donation of the additional blood and urine samples for a future biobank is

voluntary and, will not affect the participants further, as the blood is drawn together with the blood samples drawn as part of the study and urine spots are collected in the same days as urine is collected as part of the study. Hence it will not cause an additional burden on the patient. A total of 30 ml blood will be drawn (10 ml at V1, V5 and V6) and a total of 24 ml urine will be kept (12 ml at V1 and V5) and stored in freezer at SDCC, [name]. Donation of samples to the biobank for future research is voluntary, and the participants will be asked to sign an independent informed consent regarding donation of samples to the biobank for future research. Rejection of donation of samples to the biobank, will not affect participation in the study. Acceptance from the Danish Data Protection Agency will be sought in a separate application for the biobank for future research. Before samples from the biobank for future research can be used, a study protocol will be submitted for approval by an Ethics Committee. Blood and urine samples and associated data from the research biobank and the biobank for future research belong to the study investigators.

13 Statistical methods and determination of sample size

13.1 Calculations

The average changes after week 24 and 48 in primary and secondary outcomes will be calculated for each of the three groups. Results will be presented as means (SD) for normally distributed variables and as medians (inter-quartile range) for non-normally distributed variables.

13.2 Statistical methods

Intention-to-treat (ITT) analysis will be performed as the primary analysis on all primary and secondary outcomes after the last participant has participated in the last visit. Missing values will be handled with a last observation carried forward approach for ITT analysis. Per-protocol (PP) analysis will only be performed in case of sensitivity testing.

Parametric tests (general linear models) will be used to test differences in outcomes from baseline to follow-up. Heterogeneity in responsiveness to the interventions will be tested by dividing each intervention group into smaller groups based on data distribution (medians) or clinically meaningful cut-points. If model assumptions cannot be met even after logarithmic transformation, non-parametric tests will be used. Plots of residuals versus predicted values will be used to judge normality. Metabolic patterns will be tested with multivariate statistics. Adjustment for relevant confounders will be performed. Two-sided tests will be used. *P* values of <0.05 are considered significant. The statistical programs SPSS and SAS will be used for data analysis.

13.3 Determination of sample size

Allowing for drop-outs (~30%) and subgroup analyses we plan to include a total of 226 patients in our study. This is based on sample size calculations which suggested that including 87 participants in each of the study groups would give us 80% power to detect a clinically meaningful difference in change in HbA1c of 3.0 mmol/mol between the BCC group versus the control group with a 5% significance level using a two-sided test and an estimated standard deviation (SD) of 7 mmol/mol. This SD and dropout rate have previously been used for sample size calculations and were similar to what we found when evaluating our BCC courses on dropout rate, mean changes and SD of HbA1c after 6 months in completers with T2D. MAGE has only been used as an outcome measure of glucose variability in a few randomized controlled dietary intervention studies of patients with diabetes (40, 41) showing differences in changes in MAGE up to 4.8 mmol/l (SD: 1.0) after a 12-week carbohydrate counting intervention (40). By including 113 participants in each study group we will have a power of 80% (alpha level of 0.05) in a two-sided test to detect a clinically meaningful difference in the change in MAGE during the intervention period (24 weeks) of \geq 0.30 mmol/l (SD 0.7 mmol/l) between the study groups as presented in **Table 5**.

Difference in HbA1c, mmol/mol (SD 7.0)	Difference in MAGE, mmol/l (SD 0.7)	Net no of participants in the study (BCC vs control)	No of participants given a dropout rate of 30%
2.0	0.20	388	504
3.0	0.30	174	226
3.5	0.35	128	166
4.0	0.40	100	130

Table 5: Sample size calculations

14 Data management

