9.8 Randomisation

Participants eligible for inclusion in the study according to the screening will have the baseline measurements collected followed by a randomization carried out by the study investigator/study personnel.

A total of 226 participants will be randomly allocated in a 1:1 ratio to one of the following groups:

- 1) BCC
- 2) Control

Randomization will be performed by the investigator at visit 1 (V1) after the baseline examination. Participants will be randomly assigned to one of two groups with a 1:1 allocation by use of a computer-generated randomization schedule using the software system REDCap. The randomization list will be generated and kept securely by the clinical responsible investigator. The randomization is done by stratifying the participants based sex, BMI and HbA1c at baseline. The randomization is done in blocks to ensure an equal number of participants in each group.

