Secondary objectives were to describe changes associated with the intervention on other clinically relevant metabolic changes (body weight, body composition, blood pressure and lipid profile), changes in skills related to numeracy and carbohydrate estimation accuracy as well as on psychosocial and behavioural outcomes at the end of the intervention period and after 6 months of follow-up to assess long-term maintenance.

Hypotheses for the primary outcomes:

1. We hypothesize that BCC is superior compared with usual dietary care as stand-alone treatment (the control group) in reducing HbA1c or MAGE from baseline to end-of-treatment at week 24 (from V1 to V2).

Superiority is claimed if:

- a. the 95% confidence interval for the estimated difference in change between the groups for HbA1c or MAGE, estimated using a baseline corrected linear mixed model, excludes 0 and the P-value is <0.05: and,
- b. the estimated difference in HbA1c or MAGE between the two groups is equal to/surpass the minimal important difference in favour of the BCC group.

Hypotheses for the secondary outcomes can be found in the study protocol and clinicaltrials.gov.

Section 3: Study Methods

Trial design

Single-centre parallel-group, randomized controlled, open-label, superiority trial. Allocation ratio 1:1 to either BCC or control (usual dietary care).

Randomization

Participants were randomized using block randomization by stratifying participants based on sex, BMI and HbA1c at baseline. The randomization list was generated by an external statistician and uploaded to the electronic data management system REDCap (8.10.18, Vanderbilt University, TN, USA). Participants eligible for inclusion in the study according to the screening were randomized at the end of the screening visit (V0) by the study investigator/study personnel using the randomization module in REDCap. Baseline measurements were collected at the following baseline visit (V1) for all participants.

Sample size

See study protocol.

Framework

Superiority trial. See Objectives section.

Statistical interim analyses and stopping guidance

No interim analyses were planned and no guidelines for terminating the trial early was made.

Timing of final analyses

The results will be analysed when this statistical analysis plan has been uploaded at clinicaltrials.gov

Timing of outcome assessments

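### The 30% drop-out allowance multiplies by 1.3 instead of dividing by 0.7, so 226 enrolled gives about 76% power, not 80%, at the stated drop-out rate

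*Protocol*

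**What the plan says.** Protocol section 13.3 sizes the trial on a "clinically meaningful difference in change in HbA1c of 3.0 mmol/mol between the BCC group versus the control group". The assumed SD is 7 mmol/mol and the test is two-sided at 5%. On that basis it finds that "including 87 participants in each of the study groups would give us 80% power". It then moves to the number enrolled: "Allowing for drop-outs (~30%) and subgroup analyses we plan to include a total of 226 patients in our study".

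Table 5 has one column for the net total and one headed "No of participants given a dropout rate of 30" per cent. The row for 3.0 mmol/mol, which is also the row for 0.30 mmol/l in MAGE, reads 174 net and 226 enrolled. For MAGE (SD 0.7) the text says: "By including 113 participants in each study group we will have a power of 80" per cent.

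The figure of 226, 113 per group, is repeated in sections 9.2 and 9.8 ("A total of 226 participants will be randomly allocated in a 1:1 ratio to one of the following groups"). Section 9.5.3 says that participants are not replaced. The SAP's entry under Sample size is only "See study protocol", so the protocol figures remain the operative ones.

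**The concern.** A drop-out rate is a proportion of those enrolled. To keep 174 participants after losing 30%, enrolment must be 174 / 0.7. The protocol appears to have added 30% of the net number instead, which covers a smaller loss than the one it names.

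The section also attaches 80% power to two different group sizes, 87 for HbA1c and 113 for MAGE, although both outcomes share one row of Table 5 and the same standardised effect. And it says that 226 leaves room for subgroup analyses, which cannot be so if 226 does not cover drop-out.

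At stake is the power claim for both primary outcomes. A report stating 80% power with allowance for 30% drop-out would be inaccurate, and a null result would be read against a power that the design does not have on its own method.

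**Working it through.** **Inputs** (Protocol 13.3 and Table 5): difference 3.0 mmol/mol, SD 7; MAGE difference 0.30 mmol/l, SD 0.7; two-sided alpha 0.05; target power 80%; drop-out 30%; allocation 1:1. The standardised effect is 3.0/7 = 0.30/0.7 = 0.4286 for both outcomes, so one calculation serves both.

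**Step 1: reproduce the net figures.** With n per group, the two-sample t statistic has 2n − 2 degrees of freedom and noncentrality difference / (SD × √(2/n)). The smallest n giving at least 80% power is:

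| Difference (SD 7) | n per group | Total | Table 5 net |
|---|---|---|---|
| 2.0 | 194 | 388 | 388 |
| 3.0 | 87 | 174 | 174 |
| 3.5 | 64 | 128 | 128 |
| 4.0 | 50 | 100 | 100 |

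All four rows match exactly. Power at 87 per group is 80.3%.

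**Step 2: find how the enrolled figures were made.**

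| Net | Net × 1.3 | Table 5 enrolled | Net / 0.7 | Rounded up to equal groups |
|---|---|---|---|---|
| 388 | 504.4 | 504 | 554.3 | 556 |
| 174 | 226.2 | 226 | 248.6 | 250 |
| 128 | 166.4 | 166 | 182.9 | 184 |
| 100 | 130.0 | 130 | 142.9 | 144 |

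Every enrolled figure is net × 1.3, rounded to the nearest whole number. None agrees with net / 0.7.

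**Step 3: what 226 delivers.**
- After 30% loss: 226 × 0.7 = 158.2, or 79 per group.
- Noncentrality at 79 per group: 3 / (7 × √(2/79)) = 3 / 1.114 = 2.69. Power is 76.3%, so the type II error is about 24% rather than 20%.
- Difference detectable with 80% power at 79 per group: 3.14 mmol/mol.
- Largest loss that still leaves 174: 1 − 174/226 = 23.0%.
- The other three rows of Table 5 also fall to 76–77% after 30% loss.

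**Step 4: the MAGE sentence.** If 113 per group are analysed, power is 89.4%. If 113 are enrolled and 30% are lost, it is 76.3%. Neither is 80%, which belongs to 87 analysed per group.

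**Step 5: subgroups.** Drop-out alone needs 250 in equal groups, 24 more than planned (250 − 226). No part of the 226 is a reserve for subgroup analyses.

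**The case against.** The strongest reply is that 76% understates the power of the analysis that will be run. It assumes a plain t test in which drop-outs contribute nothing. Protocol 9.5.3 plans follow-up of withdrawn participants who agree, so not every withdrawal is a missing outcome. The SAP's primary model is baseline-corrected and adjusts for the stratification variables. If SD 7 is the SD of the change, and baseline and week-24 variances are equal with correlation r, baseline correction multiplies the variance by (1 + r)/2. Power at 79 per group would then be about 87% at r = 0.5, 83% at 0.7, 80.6% at 0.8 and 78% at 0.9.

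This stands as a reason to state the basis of the 76%. It does not rescue the calculation: the documents give no r, section 13.3 claims no such gain, and the section itself sizes the trial on participants left after drop-out. The last-observation-carried-forward rule in Protocol 13.2 keeps records but adds no week-24 measurement. In the SAP model, someone lost before week 24 who does not return supplies only a baseline value, and MAGE is not measured at the later follow-up visit.

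The approximate sign before 30% does not explain the figure either. The Table 5 column names 30% without qualification and every row follows × 1.3. Nor was 30% only a cautious margin: the protocol says that it was similar to the rate seen in the centre's own courses.

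It is also fair that 113 in the MAGE sentence may mean the number enrolled. The sentence is then the same slip repeated rather than a second error, but it still needs correcting.

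Finally, the SAP writes of randomisation in the past tense, so enrolment appears to be closed, and no estimate, test or analysis set changes. That limits the consequence to what is reported about power.

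**Conclusion.** The error is real and systematic. The net sizes are right; the drop-out allowance is wrong in all four rows of Table 5. With 226 randomised and 30% lost, 79 per group remain and power is 76.3% for either primary outcome; 80% holds only up to 23% loss. The shortfall is about 4 percentage points of power, or 24 patients, and does not invalidate the trial.

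The 76% rests on the protocol's own assumptions: a two-sided 5% two-sample t test, the stated differences and SDs, equal loss in the two groups, and no week-24 data from drop-outs. It is the power of the significance test only. The SAP's further requirement, that the estimated difference reach the minimal important difference, is a separate matter that this figure does not cover.

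**What to change.** Replace the SAP's cross-reference under Sample size with a corrected statement, and use the same wording in the report. For example:

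*With 226 randomised and 30% drop-out, 158 participants (79 per group) are expected to be evaluable. A two-sided 5% t test, with drop-outs contributing no week-24 data, then has 76% power for a difference of 3.0 mmol/mol in HbA1c (SD 7) or 0.30 mmol/l in MAGE (SD 0.7). Power of 80% requires 87 evaluable per group, that is, drop-out of at most 23%.*

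In addition:
- Correct the last column of Table 5 to net / 0.7, rounded up to equal groups: 556, 250, 184, 144.
- Attach the 80% in the MAGE sentence to 87 evaluable per group, not to 113.
- Delete the reference to subgroup analyses as a reason for the 226. If the subgroup analyses are mentioned there at all, say that no sample size was reserved for them.

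The cost is wording, and a stated power that is slightly less favourable. No further patients are needed and the analysis does not change.
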